We will analyze and compare cancer serum peptidomes using two different mass spectrometry platforms, MALDI-TOF and LC-MS (MS/MS), each at two different locations, the [name] Lab at MSKCC and the [name] Lab at New York University (NYU); i.e., the *NY consortium*. Four standalone instruments will therefore be used in the work described in this proposal. Systematic performance and reproducibility comparisons will be carried out between the two instruments of platform and between the two platforms.

Serum peptide samples are prepared for MALDI-TOF MS analysis using an automated liquid handling system, to form a fully integrated and previously optimized platform (Appendix A). A mirror robot/MALDI platform is established at NYU, with identical liquid handler but from a different manufacturer. Conversely, a capillary liquid chromatography (cLC) system coupled to an electrospray (ESI) hybrid quadrupole (Q)-TOF mass spectrometer will first be tested and optimized for serum peptidome analysis at NYU, and then accurately copied at MSKCC using a cLC system and Q-TOF mass spectrometer from different manufacturers.

IRB
PB

Amended: 2/1/12

Memorial Sloan-Kettering Cancer Center IRB Protocol

IRB#: 08-114 A(4)

While in general the throughput of LC-MS is lower than that of MALDI-TOF, we feel that it will be very useful to use LC-MS to evaluate the biomarker discovery platform using MALDI-TOF. We anticipate that LC-MS based peptide quantitation should provide greater depth of coverage of the peptidome than MALDI-TOF because of the extra dimension of analysis provided by separating proteins into subgroups direct coupling of HPLC to the mass spectrometer. In addition, LC-MS will enable rapid identification by MS/MS of peptides of interest- i.e., those that have diagnostic value for differentiating between disease and control groups. The [name] lab has extensive experience in using nanoflow HPLC-Q-TOF LC-MS/MS for the identification and relative quantification of proteins and peptides.

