Three MS-based approaches will be established, optimized and applied to serum peptidome profiling and to plasma functional proteomics (i.e., protease activities) with a peptidomic read-out. The standard (S) approach we have taken until recently uses normalized MALDI ion intensities of the peptides for discriminant analysis and diagnostic peptide-signature discovery.¹² The same approach is commonly used in LC-MS-based proteomic profiling, but so far only for tryptic peptides, not for the serum peptidome. While we have compelling evidence that MALDI-based peptide ion-signatures can differentiate cancer samples from controls¹², relative quantitation of the relevant peptides by comparing the ion intensities to those of added, non-degradable, isotopically labeled reference peptides may make the data more consistent within data sets and reproducible over time. We will henceforth refer to this approach as “quantitative profiling” (Q). Relative quantitation of serum peptides of interest can be done by comparing the MS-ion intensities to those of added, isotopically labeled reference peptides, having the exact same sequence and otherwise same chemical properties as the endogenous ones (i.e. distinguishable by molecular mass only). As such, all peptide pairs will display the exact same MALDI-ionization characteristics. Comparing ion intensities will therefore provide a means of normalizing the values for each peptide. While it does not provide absolute quantification in the absence of accurate calibration curves, it is an accepted way of expressing relative concentrations, or ratios, of two analytes. As reported, cancer serum peptide-signatures are surrogate markers for tumor-derived proteases.¹² Exogenous synthetic substrates, identical to the founder of each nested set of serum peptides, should degrade in an equal manner as the endogenous ones after addition to serum or plasma, with the important distinction that proteolysis can be readily controlled in terms of time, temperature and added amounts of substrates. Coupled to a MALDI read-out, such analyses amount to a blood “protease assay” (A) to monitor the tumor-dependent activities inferred from our prior studies. As explained above, addition of non-degradable reference peptides, will then also enable relative quantitation.

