MALDI-TOF MS-based Standard Profiling (S): 500 samples from men undergoing prostate biopsy (estimated 150 malignant; 350 benign) will be analyzed. The number of MALDI-based analyses will be as follows: 500 samples x 3 independent analyses over

IRB
PB

Amended: 2/1/12

Memorial Sloan-Kettering Cancer Center IRB Protocol

IRB#: 08-114 A(4)

time = 1500 MALDI-analyses per site; 3000 analyses for both sites combined. Feature selection and class prediction will be performed on the data generated from these samples. Additionally, reproducibility will be checked.

MALDI-TOF MS-based Quantitative Profiling (Q): A random selection of 200 serum samples (100 malignant; 100 benign) will be analyzed at two time points at both *NY consortium* sites. These 200 samples will be the same samples examined by the remaining technologies. The number of analysis will therefore be: $200 \times 2 = 400$ per site; 800 for both sites combined. Statistical and reproducibility analysis will be same as described above

MALDI-TOF MS-based Protease Assays (A): A random selection of 200 serum samples (100 malignant; 100 benign) will be analyzed at two time points at both *NY consortium* sites. These will be the same as the “Q” samples above. The number of analysis will therefore be: $200 \times 2 = 400$ per site; 800 for both sites combined. Statistical and reproducibility analysis will be same as described above

LC-MS Ion Intensity-based Standard Profiling (S): The NYU site will use the optimized LC-MS protocol to analyze sera from 100 patients with prostate cancer on biopsy and sera from 100 patients with a benign prostate biopsy. These will be the same as the “Q” samples above. Both the NYU and MSKCC will analyze each sample, and all analyses will be repeated 3 months later for a total of $(100 + 100) \times 2 = 400$ analyses performed at each site. All statistical analyses, including classification and comparison of repeat analyses at each site as well as results between sites, will be performed.

LC-MS Ion Intensity-based Quantitative Profiling (Q): A random selection of 100 malignant and 100 benign serum samples will be analyzed for a total of 200 LC-MS runs at both sites. These will be the same as the “Q” samples above. Evaluation of whether inclusion of the labeled standard peptides improves the sensitivity and specificity of the analyses will be performed.

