Sample size considerations for the prediction rules are based on the AUC. The methods used here were introduced by Pepe.¹⁸ Since the known biomarkers, such as PSA, give an AUC of approximately 0.8, our goal in Aim 1 is a prediction rule with an AUC of greater than 0.8. For the validation set of size 250, fixing the type I error rate at 0.05, the true AUC would have to be at least 0.86 to have at least 80% power. This is based on a one sample test. In Aim 2, we are comparing the AUC of combining the standard biomarkers with proteomic data to just using the biomarkers. In this case, the AUC of the biomarkers plus proteomic model would have to be at least 0.89 to have at least 80% power. This is a two sample test. While the data are paired, we follow Pepe’s recommendation¹⁸ to treat the samples as independent for sample size determination because the correlation is unknown without pilot data and treating the samples as independent is conservative.

In addition to prediction, the association between peak intensity and group membership (“cancer” vs. “no cancer”) will be evaluated for every bin using the Wilcoxon rank sum test or Fisher’s exact test, depending on whether the data is being treated as continuous or binary. Adjustment will be made for multiple comparisons using the false discovery rate methods of Benjamini and Hochberg.¹⁹ Finally, the data will be hierarchically clustered to examine whether there are distinct peptide patterns associated with subsets of samples.

IRB
PB

Amended: 2/1/12

Memorial Sloan-Kettering Cancer Center IRB Protocol

IRB#: 08-114 A(4)

The full set of 500 samples will be examined using the standard MALDI technique at MSKCC. Thus, the main prediction rules that will be reported will be for these samples using this method at this site. As there are three time points, three separate rules will need to be reported and compared as discussed below. In addition, all data sets will be simultaneously processed in order to get the same sets of bins for reproducibility comparisons. Two other MALDI methods and two LC-MS methods will be used on a subset. For each, the same subset of 100 malignant samples and 100 benign samples will be examined. The same analyses as on the full set will be undertaken, but here 50 of each will be used as a training set and 50 of each will be used as a test set.

Secondary Objectives:

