The proteomic profiles of Caucasian men and of African-American men will be compared to see if the same peaks that are predictive in one are predictive in the other. In addition, the AUCs for the two groups will be compared based on models that use all the data.²⁰ Finally, separate models will be built for the two groups and the AUCs will again be compared.

As mentioned in section 4, we distinguish two aspects of reproducibility: *analytical* reproducibility, that is, whether a proteomics machine produces similar peaks on repeated samples, and *inferential* reproducibility, whether a proteomics experiment produces similar conclusions when repeated.

The basic method for assessing analytic reproducibility will be through the concordance correlation coefficient (CCC)²¹ of the intensity estimates. This CCC is a measure of the agreement between two readings of the same sample via the variation from the 45 degree line through the origin. It is on the same -1 to 1 scale as the standard Pearson correlation. Since there are about 600 bins per sample, there will be 600 CCCs for every comparison. Therefore, we will compute summary statistics of the CCCs. These summaries will be based on all the bins and just the discriminating bins. Since the statistic is only pair-wise, different analyses will have to be done for the three time points, the two sites, and the two platforms (MALDI and LC-MS). The only comparison between the platforms will be between standard MALDI and standard LC-MS.

Inferential reproducibility will consist of two components: determination of whether the same peaks are discriminating and comparisons of the AUCs for the prediction of cancer or no cancer. These comparisons will be made for the same varying conditions as for analytic reproducibility. For the former, discriminating peaks will be identified using a variety of thresholds and the differences will be reported as summary statistics. For the latter, formal testing of differences in AUCs will be undertaken, as well as summary statistics. A question of particular interest will be whether the difference in the estimated AUC from the two sites using the standard MALDI platform is statistically significant.

IRB
PB

Amended: 2/1/12

Memorial Sloan-Kettering Cancer Center IRB Protocol

IRB#: 08-114 A(4)

The last two secondary aims involve collection of material for future studies and no current data analyses.

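### For standard MALDI versus standard LC-MS, a per-bin CCC alone cannot tell analytic disagreement from a different intensity scale; report its correlation and bias parts separately

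*Combined protocol and SAP*

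**What the plan says.** Under Secondary Objectives, Section 11.0 makes the CCC the basic tool for analytic reproducibility and describes it as a "measure of the agreement between two readings of the same sample via the variation from the 45 degree line". One CCC is computed per bin, about 600 per comparison. These are summarised over all bins and over the discriminating bins. The same statistic serves the three time points, the two sites and the two platforms. For platforms, "The only comparison between the platforms will be between standard MALDI and standard LC-MS".

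On putting the data on a common footing, the documents say three things:

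- Section 11.0 aligns the bins: "all data sets will be simultaneously processed in order to get the same sets of bins for reproducibility comparisons".
- Section 4.2 says the standard approach "uses normalized MALDI ion intensities of the peptides for discriminant analysis and diagnostic peptide-signature discovery". It cites an earlier paper and does not itself describe the normalisation.
- Section 4.2 describes a separate quantitative approach (Q), in which each peptide is compared with a labelled reference of the same sequence: "Comparing ion intensities will therefore provide a means of normalizing the values for each peptide". Q is not part of the platform comparison.

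The platforms are different measuring systems. MALDI uses laser desorption (Section 3.0). The LC-MS system is a chromatograph "coupled to an electrospray (ESI) hybrid quadrupole (Q)-TOF mass spectrometer will first be tested and optimized for serum peptidome analysis at NYU". Section 4.2 also says that the second site's counterpart systems, for MALDI and for LC-MS, involve different manufacturers.

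**The concern.** The CCC penalises any departure from the identity line, including a constant multiplicative difference in signal. Between repeat runs on one instrument such a shift is itself a failure of reproducibility, and the penalty is wanted. Between laser-desorption and electrospray instruments, a given peptide may simply give a stronger or weaker signal on one platform. Two platforms that rank the samples identically could then show low CCCs, and the summary over about 600 bins would not reveal the reason. Reproducibility across platforms is a named secondary objective (Section 2.2), so its main analytic measure should be interpretable.

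**Working it through.** The plan gives no CCC target, sample size or power for this comparison, so there is no figure of its own to reproduce.

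**Inputs from the documents.** A per-bin CCC around the 45 degree line, about 600 bins, and a summary over bins (Section 11.0). Both platforms are run on 200 shared samples, 100 malignant and 100 benign (Sections 4.2 and 11.0).

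**Inputs assumed.** The ratio k of intensity scales between platforms, the between-sample CV c within a bin, and the true correlation r. The documents give none of these, so ranges are shown.

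**Step 1: what the CCC contains.** With means m1, m2 and SDs s1, s2,

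CCC = 2·r·s1·s2 / (s1² + s2² + (m1 − m2)²) = r × Cb,

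where Cb is the bias factor. If one platform reads k times the other and both have CV c,

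Cb = 2·k·c² / (c² + k²·c² + (k − 1)²).

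**Step 2: scale difference only (r = 1, so CCC = Cb).**

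| k | c = 0.5 | c = 1.0 |
|---|---|---|
| 1 | 1.00 | 1.00 |
| 1.25 | 0.625/0.703 = 0.89 | 2.5/2.625 = 0.95 |
| 1.5 | 0.75/1.0625 = 0.71 | 3/3.5 = 0.86 |
| 2 | 1/2.25 = 0.44 | 4/6 = 0.67 |

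**Step 3: one value, two explanations.** A bin with r = 0.3 on equal scales has CCC 0.30. A bin with r = 0.9 has the same CCC once k reaches about 1.8 (c = 0.3), 2.4 (c = 0.5) or 3.7 (c = 1.0). Check at c = 0.5, k = 2.38: 2 × 0.9 × 2.38 × 0.25 = 1.071; 0.25 + 1.416 + 1.904 = 3.570; ratio 0.30.

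**Step 4: would a per-spectrum normalisation remove it?** The documents do not state this form of normalisation; it is assumed here. The simulation used 600 bins and 200 samples, scaled every spectrum to the same total on both platforms, and let per-bin response differ between platforms by a log-normal factor. The ranges cover bin CV 0.5 to 1.0.

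| SD of log response ratio | Median CCC, no measurement error | Median CCC, 20% measurement CV on each platform |
|---|---|---|
| 0 | 1.00 | not listed |
| 0.25 | 0.93–0.97 | not listed |
| 0.5 | 0.77–0.89 | 0.65–0.82 |
| 1.0 | 0.40–0.62 | 0.35–0.57 |

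Median Pearson and Spearman correlations were at least 0.99 without measurement error. With it, Pearson was 0.83–0.93. Scaling whole spectra makes samples comparable; it does not equalise each peptide's response on the two platforms.

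**Step 5: does the correlation give a stable reading?** In simulation at c = 0.5 and true r = 0.9, the median Pearson was 0.90 and the median Spearman 0.89 at k = 1, 2, 5 and 10. The median CCC fell from 0.90 to 0.40, 0.10 and 0.04. With 200 samples, the approximate 95% interval for one bin, tanh(atanh r ± 1.96/√197), is 0.87–0.92 at r = 0.9 and 0.17–0.42 at r = 0.3, so the shared subset separates these cases well.

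**The case against.** The strongest reply is that the normalisation is not absent from the plan. It is delegated to a cited paper and to Appendix A, which cannot be consulted here. If that method gives each bin equal location and scale on both platforms, Cb = 1 and the problem disappears. This stands as a limit on the conclusion. What remains is that the documents themselves describe per-peptide normalisation only for Q.

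The size is also wholly assumed. The results above run from no effect to a median CCC of 0.35, and nothing in the documents places the trial in that range. That stands too.

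No threshold or decision hangs on the CCC. The plan also asks whether the same peaks discriminate and whether the AUCs differ, and neither question needs a common scale. This limits the consequence, but Section 11.0 treats both as inferential reproducibility, so they do not repair the analytic measure.

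On scope, if an unstated scale is a difficulty between platforms, it is a question between sites as well, because the instruments there come from different manufacturers. That is right, and the fix covers it.

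Finally, replacing the CCC with a correlation would discard agreement in level, and other remedies are equivalent. That is also right, and it is why the fix splits the CCC and does not drop it.

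**Conclusion.** The concern holds in a limited form. For standard MALDI versus standard LC-MS, the planned per-bin CCC confounds scatter with per-peptide scale, and no step described in the documents separates them. The algebra is exact. The size rests on assumed k and CV, and is nil if the cited normalisation equalises location and scale per bin. Severity is minor: one analytic measure in one secondary objective. The main prediction rules, the peak-overlap comparison and the sample size are not affected.

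Three stronger readings do not follow from the documents:

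- A reader might infer that the platforms will be reported as discordant. The documents give no scale factors and no CCC cut-off, so the supportable claim is that a low value would be uninterpretable.
- A reader might infer that the CCC is the wrong measure throughout. For repeat runs on the same instrument a scale shift is a real failure and the CCC suits. Between sites it remains a reasonable main measure if its parts are shown.
- A reader might infer that the platform AUC test is biased because standard MALDI is trained on 250 men and LC-MS on 50 of each class. Section 11.0 says of the AUC and peak comparisons that "These comparisons will be made for the same varying conditions as for analytic reproducibility", and Section 4.2 says of the subset that "These 200 samples will be the same samples examined by the remaining technologies". The natural reading is a matched comparison on those 200. A refit of standard MALDI on them is neither stated nor excluded, so this is a matter of wording.

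**What to change.** For the cross-platform comparison, report the CCC per bin split into its two components: the Pearson correlation (precision) and the bias factor (agreement in level). Add a Spearman correlation as a check for non-linearity. Summarise all of these over all bins and over the discriminating bins, as already planned, and base the cross-platform analytic conclusion on the correlation.

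Report the same split for the between-site comparisons, but keep the CCC as the main measure there and for repeat runs on the same instrument.

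As a separate clarification, one sentence could say whether the platform AUC comparison refits standard MALDI on the training samples used for LC-MS and scores both on the same test samples.

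The cost is a sentence or two of analysis-plan wording and slightly more output. No new assays or samples are needed, since the 200 samples are already common to the methods. The drawback is that a correlation alone does not test agreement in level, so the bias factor must be reported beside it.

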2.2 Secondary Objectives

- To determine if Caucasian men and men of African-American descent with and without prostate cancer have different proteomic profiles.
- To assess reproducibility of proteomic profiles over different runs, platforms, and sites.
- To procure a DNA repository from these patients undergoing prostate biopsy for future assessment of kallikrein gene expression.
- To establish a bank of DNA, serum, and frozen lymphoblastoid cells from these patients for the purpose of enabling genetic investigations in men with a diagnosis of prostate cancer.

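### Peak-level reproducibility rests on flagged-peak lists alone, with no yardstick for equal runs and no comparison of the size of each peak's cancer effect between runs or sites

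*Combined protocol and SAP*

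**What the plan says.** Section 2.2 of the combined protocol and SAP names as a secondary objective "To assess reproducibility of proteomic profiles over different runs, platforms, and sites". Section 11.0 (Secondary Objectives) splits this into analytical and inferential reproducibility.

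The inferential part has two components: "determination of whether the same peaks are discriminating and comparisons of the AUCs for the prediction of cancer or no cancer". For the peaks, "discriminating peaks will be identified using a variety of thresholds and the differences will be reported as summary statistics". For the prediction models, "formal testing of differences in AUCs will be undertaken, as well as summary statistics", with particular interest in "whether the difference in the estimated AUC from the two sites using the standard MALDI platform is statistically significant".

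The analytical part uses the concordance correlation coefficient (CCC) of intensities, summarised over all bins and over the discriminating bins: "Since there are about 600 bins per sample, there will be 600 CCCs for every comparison".

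Under Primary Objectives, Section 11.0 also says that "the association between peak intensity and group membership (“cancer” vs. “no cancer”) will be evaluated for every bin using the Wilcoxon rank sum test". Binary data get Fisher's test instead, and Benjamini-Hochberg adjustment applies. All data sets are to be processed together so that the bins match. Section 4.2 plans three standard-MALDI analyses of all 500 samples (estimated 150 malignant, 350 benign) at each of two sites. The other methods use a subset of 100 malignant and 100 benign samples.

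**The concern.** The Wilcoxon statistic divided by the product of the two group sizes is the bin's AUC for cancer. Each run at each site therefore yields about 600 effect sizes, on matched bins and the same men. The peak-level comparison then keeps only whether each bin passes a cut. A bin near the cut can change lists by chance when nothing differs between runs. A strong bin that loses part of its effect can stay on both lists at many cuts and count as agreement.

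Neither of the other two analyses fills this gap. The CCC compares intensities, not the contrast between cancer and benign. The formal AUC test works at model level, cannot say which peaks lost signal, and compares rules that are built separately for each run.

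At stake is whether the reproducibility objective can tell a real, modest loss of cancer signal at one laboratory from the disagreement expected between equal laboratories.

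**Working it through.** **Plan's own figures.** None is given for reproducibility. The only power figures (Section 11.0) are for the prediction rules: AUC 0.86 (one sample) and 0.89 (two samples) for 80% power against 0.80 with 250 men. With 75 cancers and 175 benign, one-sided 5% and a binormal variance, I get 0.862 and 0.892, so they reproduce. They do not bear on this point.

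**Inputs from the documents.** About 600 bins; 150/350 samples for standard MALDI; 100/100 for the other methods; a Wilcoxon test per bin with Benjamini-Hochberg adjustment.

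**Assumptions (not in the documents).** 60 truly discriminating bins; mean effect 0.30, 0.45 or 0.60 SD; run-to-run correlation 0.7 to 0.9; false discovery rate 5%. A weaker laboratory has every effect multiplied by 0.85 or 0.71. For normal data AUC = Φ(d/√2), so a 15% loss moves a bin's AUC from 0.584 to 0.572 at d = 0.30 and from 0.664 to 0.641 at d = 0.60.

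**Step 1: one bin at the cut.** If its expected statistic lies exactly at the threshold, two equal runs disagree with probability arccos(r)/π. This is 25% at r = 0.7, 20% at 0.8 and 14% at 0.9.

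**Step 2: simulated list overlap of two equal runs** (shared peaks divided by peaks flagged in either).

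| Mean effect | 150/350 | 100/100 |
|---|---|---|
| 0.30 SD | 0.52-0.74 | 0.22-0.53 |
| 0.45 SD | 0.76-0.88 | 0.52-0.75 |
| 0.60 SD | 0.86-0.93 | 0.72-0.85 |

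At 150/350, a laboratory with 15% smaller effects at 0.60 SD overlaps its partner by 0.79-0.87. That is more than two equal laboratories at 0.30 SD.

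**Step 3: detecting a weaker laboratory.** Each statistic was judged against the 5% tail of its own equal-runs distribution, which the plan does not supply.

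| Scenario | Overlap | List size | Mean paired per-bin AUC difference |
|---|---|---|---|
| 150/350, effects 15% smaller | 34-79% | 37-83% | 79-100% |
| 150/350, effects 29% smaller | 94-100% | 91-100% | 100% |
| 100/100, 15% smaller, 0.45-0.60 SD | 35-86% | 56-82% | 81-100% |
| 100/100, 15% smaller, 0.30 SD | 0% | 10-26% | 31-68% |

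**Step 4: would the CCC see the 15% loss?** CCC = 2·cov/(v1 + v2 + (m1 − m2)²). Take 30% cancers, within-group variance 1 and correlation 0.9.
- Equal runs at d = 0.60: v = 1 + 0.21 × 0.36 = 1.0756 and cov = 0.9 + 0.0756 = 0.9756, so CCC = 0.907.
- Second run at d = 0.51: v2 = 1 + 0.21 × 0.2601 = 1.0546, cov = 0.9 + 0.21 × 0.306 = 0.9643 and mean difference = 0.3 × 0.09 = 0.027, so CCC = 0.905.

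A loss of contrast without added noise barely moves it.

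**Step 5: would the model-level AUC test see it?** I took a paired correlated-AUC test, two-sided 5%, 75/175 in the validation set, score correlation 0.7-0.9 and starting AUC 0.75-0.86. Power is about 22-82% for effects 15% smaller and 64-100% for 29% smaller, ignoring refitting of the rules.

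**Step 6: direction matters in the alternative.** Peaks lower in cancer have AUC below 0.5, so attenuation moves them up. I simulated 30 or 60 true bins with effects of 0.2-0.6 SD and reliability falling from 0.9 to 0.8 or from 0.8 to 0.7. With all effects in one direction, the mean paired difference has 55-95% power. With half the effects negative and no orientation it has 9-12%. Orienting each bin by its direction pooled over both runs restores it to 53-94%.

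**The case against.** The strongest reply is that the plan already has other safeguards, and that the peak list answers the question asked. Inferential reproducibility is defined as reaching similar conclusions on repetition. Which peaks are declared discriminating is such a conclusion, so instability near a cut is part of what is measured. Several cuts are planned, the list comparison is descriptive, and formal testing is reserved for AUCs. Much of this stands, and it is why the lists should stay.

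The CCC argument stands for assay noise. If a laboratory is weaker only because its reliability falls from 0.9 to 0.8 or from 0.8 to 0.7, effects shrink by only about 6% (√(0.8/0.9) = 0.943; √(0.7/0.8) = 0.935), a change of 0.003-0.009 in a bin's AUC at 0.2-0.6 SD. Comparing within-site CCCs on 500 samples would show this with about 100% power from a single bin. The argument does not extend to a loss of cancer contrast without added noise (step 4).

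A reader might infer that equal runs will look discordant. That holds for small effects or the 100/100 subset; at 0.60 SD with 150/350 the overlap is 0.86-0.93. A reader might also infer that a weaker laboratory will generally be missed. At 500 samples, one with 29% smaller effects loses about 9-21 flagged peaks and is found 91-100% of the time. The documents give no per-peak effects that would support either stronger reading.

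What remains unanswered is that the lists have no reference value, and that nothing planned compares effect sizes peak by peak.

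**Conclusion.** The point holds in a limited form. Peak-level inferential reproducibility is judged only by list membership at unspecified cuts, without an expected value for equal runs, so an observed overlap cannot be read as laboratory quality. For a laboratory with effects 15% smaller, list summaries miss 17-66% of cases at 150/350, against 0-21% for paired effects. Even these list figures assume an equal-runs reference that the plan lacks.

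The gap is confined to modest losses of cancer signal and to the smaller subset. Large losses show in the lists at 500 samples, and pure noise shows in the CCCs. The numbers rest on assumed effect sizes, number of true peaks, run correlation, false discovery level and size of loss. The absence of any per-peak effect comparison does not depend on them. This affects a secondary objective, not the primary prediction analysis.

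**What to change.** In Section 11.0 (Secondary Objectives), keep the thresholded lists as a descriptive display. For each planned run or site comparison within the same platform, on the same men, add:

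1. The paired difference in per-bin AUC for cancer, by the correlated-AUC method already cited as reference 20. Orient each bin by its direction pooled over both runs, so that peaks higher and lower in cancer do not cancel. Average over bins flagged in either run, so that selection is symmetric. Give a 95% confidence interval from resampling men, repeating the flagging and orientation in each resample.
2. The agreement (CCC or slope) of the roughly 600 bin-level effects between the two runs or sites.

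The cost is SAP wording and a little more analysis of data already to be collected, with no new samples, assays or staff. The summary is less simple than a count of shared peaks, which can still be shown beside it.
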